## **10.0 Follow-up and Record Retention**

Study Duration will be 30 months total, with 12 months in which intervention will be provided and 18 months of follow up.

All data will be de-identified prior to any analyses and data sharing. Data from the study will eventually be published but no identifiers will be mentioned as they will be kept separate once the collection of data is complete. Only authorized study personnel will have access to this information. PHI will no longer be accessed upon closure of the study, at which point any patient identifiers in the database will be deidentified.

Paper versions of any data will be destroyed upon completion of the study.

Electronic data will be stored indefinitely in a secured server using the RedCAP system.

## 1. INTRODUCTION

This document describes the statistical analysis plan (SAP) for a single center, stepped wedge, randomized, pragmatic, clinical trial of an intervention to remove low risk penicillin allergy labels using a single dose amoxicillin challenge. The intervention is deployed at the medical unit level, led by a unit pharmacist. Persons on the unit with a penicillin allergy label undergo a risk assessment, and low risk patients who consent to the procedure are presented with an oral amoxicillin challenge.

At the study outset, all participating units were naïve to the process for removing penicillin allergies. After the run-in period, medical units transitioned from the control condition to the intervention condition at monthly intervals. Medical units at VUMC will be randomized to determine the order in which they start the intervention.

This SAP describes the approach to analyzing the primary and secondary endpoints, as well as safety endpoints, once the trial is stopped.

## 2. PARTICIPANTS AND TREATMENT ARMS

Adult patients admitted to hospital during the 12-month study period who had 24-hour exposure to any of the study units will be included if they are not known to be pregnant. Pregnancy status is based on either documented known pregnancy via ObGyn status or BhCG results that are classified as positive using VUMC laboratory cutoffs.

Participants will be in either the control group or the intervention group, depending on when they presented to the hospital, and which hospital unit they were exposed to. Specifically:

- Control Group: Any patient who did not have a 24-hour exposure to a study unit where the intervention was active but did have at least 24-hour exposure to a control unit. The current standard of care in hospitalized patients with reported penicillin allergy is to do nothing, with all care at the discretion of the primary team. Hence, no intervention will be provided.
- Intervention Group: Any patient who had a 24-hour exposure to a study unit at any time where the intervention was active. The intervention includes systematic identification those with a penicillin allergy, application of a penicillin allergy risk stratification tool, and use of an oral amoxicillin test dose challenge order set for patients who stratify as low risk. The risk stratification tool has been demonstrated retrospectively to have a >99% (95% CI 96.4,99.9) negative predictive value for the presence of penicillin allergy in those who stratify as low risk. Test dose challenges with amoxicillin are a recommended part of routine practice in patients who report allergy but have symptoms that are low risk for true or ongoing allergy. When a unit crosses over and becomes a “live” unit with the intervention, a patient who was already admitted on the unit needs to be present for 24 hours afterward to be considered exposed to the intervention.

## 3. ENDPOINTS

### Primary endpoint

The primary endpoint for this trial is the proportion of penicillin allergy labels that are listed at admission in the chart (allergy box or problem list) but are removed from the chart before discharge (from both the allergy box and the problem list).

The primary outcome is a binary variable, either penicillin allergy label removed yes or penicillin allergy label removed no.

### Key secondary endpoints

The secondary endpoints for this trial include the following:

1. Tolerance of an amoxicillin oral challenge, which will be documented using a smart phrase to indicate tolerance or intolerance. This outcome is a binary variable, either yes= tolerated, or no =not tolerated, with relevant symptoms to be determined by chart review.
2. Uptake of the risk stratification tool: This is determined by whether patients with a penicillin allergy label in their chart receive a risk assessment. This is a binary variable, either the patient did or did not receive a risk assessment of their penicillin allergy.
3. Amoxicillin adverse events: In patients who did not tolerate their amoxicillin oral challenge, we will assess the types of adverse events that were reported.
  - a. An immediate allergic amoxicillin challenge adverse event will be defined as an adverse event reported in association with the amoxicillin challenge that includes symptoms of anaphylaxis or rash, with onset within 6 hours of the challenge dose being given.
  - b. A non-immediate allergic amoxicillin challenge adverse event will be defined as an adverse event such as rash that is potentially consistent with allergy, occurring within 24 hours of the dose being given.
  - c. A non-allergic amoxicillin challenge adverse event will be defined as an adverse event, such as gastrointestinal upset, reported in association with amoxicillin challenge, within 6 hours of the challenge dose being given.
4. Communication about penicillin allergy label removal in the discharge summary: This is determined by the presence of language about the penicillin allergy evaluation, challenge, and removal, in those patients who underwent penicillin allergy challenge. The outcome is a binary variable, as this information is either present, or absent.
  - a. This data will be obtained by manual chart review.
  - b. A smart phrase has previously been created that was encouraged to be used for this purpose, and its utilization will be extracted.
5. Longer term penicillin allergy label removal, over 3 months and 18 months of follow up. Among those who underwent a penicillin allergy label removal, whether the allergy remains out of the chart or is “ever/never” re-entered into the chart. The outcome is a binary variable at either 3 months or at 18 months.
6. Time to penicillin allergy return: for those participants who underwent an allergy label removal, we will compare the time to return of the allergy label based on the date the label first re-appeared in the chart.
7. Antibiotic utilization: This is based on the presence of qualifying penicillin or cephalosporin treatment doses, during the same hospitalization, and at 3 months and 18 months of follow up.
  - a. Same hospitalization: Utilization of these antibiotics will be defined as “yes” or “no” during the initial hospitalization in which amoxicillin challenge could have occurred, as a binary variable.
  - b. Subsequent utilization: Utilization of these antibiotics will be defined as “ever/never” by 3 months and ever/never by 18 months of follow up, as a binary variable.
  - c. Drugs included in the definition of penicillins are predefined as:
    - i. Ampicillin
    - ii. Ampicillin/sulbactam (unasyn)
    - iii. Amoxicillin
    - iv. Amoxicillin/Clavulanate (augmentin)
    - v. Cloxacillin
    - vi. Dicloxacillin

- vii. Nafcillin
- viii. Penicillin G
- ix. Penicillin VK
- x. Piperacillin
- xi. Piperacillin/Tazobactam
- xii. Ticarcillin
- xiii. Ticarcillin/Clavulanate (timentin)

d. Drugs included in the definition of cephalosporins are predefined as:

- i. Cefadroxil
- ii. Cefprozil
- iii. Cefaclor
- iv. Cephalexin
- v. Cephalothin
- vi. Cefazolin
- vii. Cefoxitin
- viii. Cefotetan
- ix. Cefamandole
- x. Cefuroxime
- xi. Cefepime
- xii. Ceftriaxone
- xiii. Cefpodoxime
- xiv. Ceftazidime
- xv. Cefdinir
- xvi. Cefixime
- xvii. Ceftaroline
- xviii. Ceftobiprole
- xix. Ceftozolane-Tazobactam

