## Main Analysis

Prior to modeling the data, we will describe the presentation of the amoxicillin challenge, the response, any adverse events, the rate of penicillin allergy removal, and subsequent use of penicillin as follows:

- Patient response to amoxicillin challenge -as n (proportion of total PALs)
  - Pass/Fail
    - as n (proportion) of total challenges done

- Proportion of failed challenges in which hypotension was present
    - as n (proportion) of challenges failed
      - Hypotension defined as systolic blood pressure decrease of 30% compared to pre-challenge blood pressure.
- Patient allergy removed from the chart's allergy box- absent at discharge
  - as n (proportion of total PALs)
- Same hospitalization use of a penicillin antibiotic,
  - as n (proportion of total PALs)
- Adverse events associated with amoxicillin challenge,
  - as n (proportion) of total challenges
- Adverse events associated with same hospitalization use of a penicillin antibiotic
  - as n (proportion of total PALs),
- Allergy evaluation information present/absent in discharge summary,
  - as n (proportion of completed PALs assessed as low-risk)
- Number of subsequent VUMC healthcare encounters after the initial hospitalization
  - Outpatient
    - average n per patient
  - ED/observation
    - average n per patient
  - Hospitalization/Inpatient
    - average n per patient
  - Surgical
    - average n per patient
- Ratio of penicillin treatments per total patient healthcare encounters since study entry

**Primary model:** Penicillin allergy label removal will be compared between the two groups using an adjusted logistic regression mixed effects model. In addition to study group assignment, the model will be adjusted for the following baseline covariates: time from start of study, age, race/ethnicity, sex, comorbidity index, health literacy, and intervention unit as a random effect. We will additionally include intervention unit general acuity level, defined based on the average APRDRG for patients discharged from the unit during the study period. The magnitude of effect will be reported as odds ratios with confidence intervals. A critical two-sided p-value of 0.05 will be used to draw conclusions on the main effect of intervention.

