### **Analysis of secondary endpoints**

We will proceed with exploring the effect of low-risk penicillin allergy challenge on secondary endpoints in a similar manner as for the primary endpoints:

- i) Endpoints will be described as medians and interquartile ranges or frequencies and proportions
- ii) Binary variables will be compared using an adjusted logistic regression, and ordered or continuous variables will be compared using proportional odds logistic regression
- iii) The odds ratios with confidence will be reported as estimates of effect size.
- iv) Secondary endpoints will be modelled with adjustment for baseline covariates; sensitivity analyses will exclude adjustment and may include imputation for any missing outcomes.
- v) Differential treatment effects will be evaluated using the interaction term, and consequent differential effects reported
- vi) Time to return of penicillin allergy labels will be evaluated using a Cox proportional hazards model with covariate adjustment.

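### Label durability and time to label return are assessed only among de-labelled patients; as an arm contrast this is selected on the primary outcome and rests on about 3–5 expected controls

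*SAP*

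**What the plan says.** The SAP's primary endpoint is "the proportion of penicillin allergy labels that are listed at admission in the chart" and removed before discharge. Its denominator is therefore everyone labelled at admission.

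Two key secondary endpoints use a smaller set:

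- Item 5 (status at 3 and 18 months): "Among those who underwent a penicillin allergy label removal, whether the allergy remains out of the chart".
- Item 6 (time to return): "for those participants who underwent an allergy label removal, we will compare the time to return of the allergy label". It does not say which groups are compared.

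The SAP section on analysis of secondary endpoints opens by "exploring the effect of low-risk penicillin allergy challenge on secondary endpoints in a similar manner as for the primary endpoints". It then plans description ("Endpoints will be described as medians and interquartile ranges or frequencies and proportions"), a model for binary endpoints ("Binary variables will be compared using an adjusted logistic regression") and a model for time to return ("Time to return of penicillin allergy labels will be evaluated using a Cox proportional hazards model with covariate adjustment"). The primary analysis it refers back to reads: "Penicillin allergy label removal will be compared between the two groups using an adjusted logistic regression mixed effects model".

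SAP section 9 assigns the intent-to-treat set to all secondary efficacy analyses and does not mention the de-labelled subset. The SAP's sample-size section says that the data will be enough to report secondary outcomes precisely.

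**The concern.** Whether a label is removed is decided after randomisation and is what the intervention tries to change. Controls enter the de-labelled set through rare removals at the primary team's discretion. Intervention patients enter mainly through systematic identification, risk stratification and challenge (SAP section 2). The two groups of de-labelled patients can therefore differ in allergy history, certainty of the removal and documentation, whatever the effect of the intervention on durability. The covariates in the primary model (calendar time, demographics, comorbidity, health literacy, unit and unit acuity) do not include allergy history or risk stratum, so adjustment does not restore comparability.

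The second problem is information. The control removal rate is assumed to be very low, so the control side of the contrast is a handful of patients. A published hazard or odds ratio from it would be read as a trial effect on durability, although it would be neither randomised nor well estimated.

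**Working it through.** **Plan's own figure.** The documents give no expected number of de-labelled controls. Their only sample-size figure, 35 per group, concerns removal itself. A two-sided pooled test of proportions gives 36 for 0.5% v 20.5% (SAP control rate plus 20 points) and 35 for 0.1% v 20.1% (protocol control rate plus 20 points). It says nothing about the de-labelled subset.

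**Inputs.**
- 12 units with one-month steps (SAP section 8); one cluster live at the outset (protocol section 4.0).
- 10–15 labelled patients per unit per month (SAP section 8); 15–20 per month on the unit described in protocol section 8.0, applied here to all units.
- Control removal 0.5% (SAP) or 0.1% (protocol).
- Intervention removal 10% (pessimistic) or 20.5% (0.5% plus the 20-point target).
- Return rate: not given. I assume 10–20% by 18 months and also show 40–50%.

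**1. Unit-months.** Control: 0+1+…+11 = 66. Intervention: 1+2+…+12 = 78. The SAP mentions a run-in without a length; one all-control month would give 66+12 = 78 control unit-months.

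**2. Expected de-labelled patients.**

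| Case | Calculation | Result |
|---|---|---|
| Controls, SAP inputs | 66×10×0.005 to 66×15×0.005 | 3.3 to 4.95 |
| Controls, one all-control month | 78×10×0.005 to 78×15×0.005 | 3.9 to 5.85 |
| Controls, protocol inputs | 66×15×0.001 to 66×20×0.001 | 0.99 to 1.32 |
| Intervention, SAP inputs | 78×10×0.10 to 78×15×0.205 | 78 to 240 |

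The SAP-based control counts lean high. The observed 0.5% also counts test dose challenges, and patients exposed to both conditions are classed as intervention.

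**3. Chance of no control return.** With a Poisson number of control removals (mean m) and return rate r, this is exp(−m·r).
- r = 10–20%: exp(−3.3×0.1) = 0.72 to exp(−4.95×0.2) = 0.37.
- r = 40–50%: exp(−3.3×0.4) = 0.27 to exp(−4.95×0.5) = 0.08.

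With no control return, the odds or hazard ratio has no finite estimate.

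**4. Precision when there is a control return.** The unadjusted 95% limits are the ratio multiplied and divided by exp(1.96·√(1/d_c + 1/d_i)), where d_c and d_i are control and intervention returns. Take d_i from 8 (78×0.1) to 48 (240×0.2). One control return gives a factor of 8.0 to 7.2; two give 4.7 to 4.1.

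**5. A bound that needs no return rate.** Suppose every removed label returned. By the Schoenfeld formula, power = Φ(√(D·a(1−a))·ln 2 − 1.96) for a hazard ratio of 2, with D the total returns and a the control share.
- D = 3.3+78 = 81.3, a = 0.041: power 0.23.
- D = 4.95+239.85 = 244.8, a = 0.020: power 0.33.

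The hazard ratio detectable with 80% power is about 3.6–4.8.

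**6. Description in the de-labelled set.** Illustrative exact 95% intervals: 8/78 gives 4.5–19.2%; 24/240 gives 6.5–14.5%.

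**7. Whole-denominator alternative.** Labelled patients: 780–1,170 intervention and 660–990 control. For the outcome of label removed before discharge and still absent at 18 months, with 10% removal and 10–20% return:
- Intervention 0.10×(0.8 to 0.9) = 8.0–9.0%; control 0.005×(0.8 to 0.9) = 0.40–0.45%; difference 7.6–8.6 points.
- 95% half-width 1.96·√(p_i(1−p_i)/n_i + p_c(1−p_c)/n_c) = 1.6–2.1 points ignoring clustering, or 2.8–3.6 at an assumed design effect of 3 (×√3).
- Expected control events 660×0.0040 = 2.6 to 990×0.0045 = 4.5; chance of none exp(−2.64) = 7% to exp(−4.46) = 1%.

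**The case against.** The arm contrast is inferred. Item 5 contains no comparison, item 6 names no groups, and the Cox sentence says only that return will be evaluated. The secondary-analysis section is a general template introduced as exploring the effect of challenge. It cannot be a literal arm contrast for every endpoint, because challenge tolerance, challenge adverse events and discharge communication are defined by the challenge. Description is already planned, and the SAP puts effect sizes ahead of significance for secondary analyses. The protocol's own aim, durability following removal, is conditional on removal.

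Much of this stands. A reader might infer that the SAP expressly commits to comparing durability by arm; it does not, and the point is conditional on that reading. But item 6 does say that a comparison will be made, and the plan attaches ratio models that refer back to a two-group analysis. The other candidate, challenged versus unchallenged patients, is not randomised either. Emphasising effect sizes does not help when the effect size is what is selected and unstable. The protocol's conditional question is a reason to describe the de-labelled patients; it does not call for a between-arm model.

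A reader might also infer that the SAP's assurance on precision is wrong in general. The documents do not support that: it speaks of reporting, and step 6 shows that description is reasonably precise. It fails only for this contrast.

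**Conclusion.** The point holds in conditional form. If items 5 and 6 are analysed by arm, as the SAP most naturally implies, the resulting ratios are selected on a post-randomisation event and depend on about 3–5 expected controls (up to 5.9 with one all-control month, about 1.0–1.3 on the protocol's inputs). Low power does not depend on any assumed return rate. The primary conclusion is unaffected.

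A reader might infer that the ratio will usually be inestimable. The documents do not support that, because they give no return rate: the chance of no control return is 37–72% at an assumed 10–20% return but 8–27% at 40–50%. Nor is it likely on the SAP's inputs that no control is de-labelled at all. That chance is 0.7–3.7% (binomial, 990 and 660 controls), against 27–37% on the protocol's inputs (exp(−1.32) and exp(−0.99)).

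These figures assume the wedge layout in step 1, equal recruitment across units, and that removal in items 5 and 6 means removal before discharge, as in the primary endpoint.

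**What to change.** 1. Do not fit or interpret a between-arm logistic or Cox model in the removed-only subset.
2. Among de-labelled patients, describe re-labelling at 3 and 18 months and time to return, with death treated as a censoring or competing event. State in SAP section 9 that these descriptions use the de-labelled subset.
3. If an arm comparison of durability is wanted, use all patients labelled at admission. Count months from discharge in both arms, because patients never de-labelled in either arm have no removal date. The outcome can be label removed before discharge and still absent at 3 and 18 months. To count removals after discharge as well, it can be label absent at 3 and 18 months. The second choice may matter, since protocol section 1.0 puts eventual removal in current practice at 13.4%. Report a risk difference beside the odds ratio.
4. Optional: a sensitivity description limited to patients with a later encounter at the centre, since someone never seen again counts as not re-labelled.

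Cost: SAP wording, plus a date of death if it is not already extracted. Dates of label return and later encounters are already planned. The arm-level hazard ratio is given up. The removed-and-still-absent composite mostly reflects the primary effect, and its odds ratio shares the primary model's sparse control cell.

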### **Descriptive analysis**

Initial analysis will be descriptive in nature. First, we will describe the flow of participants into the study and allocated to the two arms using a CONSORT diagram. Then, the study participants will be characterized based on demographic and clinical variables measured at the time of eligibility, unless otherwise indicated. Variables will be described using median and interquartile range or using count and percent (proportion). No statistical testing will be done to compare characteristics between groups. The following variables will be described by study arm and overall:

- Age (years)- Date of presentation-birthdate in years
- Race (categories same as for Clinical Trials.gov reporting: American Indian/Alaska Native, Asian, Native Hawaiian or Pacific Islander, Black or African American, White, More Than One Race, Unknown or Not Reported)- patient self-reported in EHR
- Ethnicity (Hispanic or Latino, Not Hispanic or Latino, Unknown or not reported)- patient self-reported in EHR

- Sex (Male or female, other, unknown)- patient self-reported in EHR
- Charlson comorbidity index
- Health literacy score- VUMC instruments- standard of care to collect for inpatients
- Unit admitted to at the time of study inclusion- first study unit on which patient spends at least 24 hours during the admission.
  - Unit on which challenge was performed- For those who received amoxicillin challenge, unit on which the testing was done.
- Penicillin allergy listed under allergies/problem list on day of admission
  - Proportion reporting allergy to any of the following indicated in Allergy field in eStar:
    - Ampicillin
    - Ampicillin/sulbactam (unasyn)
    - Amoxicillin
    - Amoxicillin/Clavulanate (augmentin)
    - Cloxacillin
    - Dicloxacillin
    - Nafcillin
    - Penicillin G
    - Penicillin VK
    - Piperacillin
    - Piperacillin/Tazobactam
    - Ticarcillin
    - Ticarcillin/Clavulanate (timentin)

Next, we will describe the fidelity of applying the intervention as follows:

- Penicillin allergy labeled patient completed risk assessment (as n (proportion) of total Penicillin Allergy Labels (PALs)
  - Highest- as n (proportion of risk assessed)
  - Higher- as n (proportion of risk assessed)
  - Low-risk allergy- as n (proportion of risk assessed)
- Patient received amoxicillin challenge as n (proportion of total PALs)
  - After qualifying as low-risk -as n (proportion of low-risk PALs)

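### The closed drug lists behind secondary endpoint 7 (antibiotic utilization) omit oxacillin, cefotaxime and cefiderocol and misspell ceftolozane-tazobactam; correct them before extraction

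*SAP*

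**What the plan says.** SAP section 3, Key secondary endpoints, item 7 defines the endpoint by qualifying drugs: "Antibiotic utilization: This is based on the presence of qualifying penicillin or cephalosporin treatment doses". It is binary at each time point. For the index stay, "Utilization of these antibiotics will be defined as “yes” or “no” during the initial hospitalization"; for follow-up, "Utilization of these antibiotics will be defined as “ever/never” by 3 months and ever/never by 18 months of follow up".

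Items 7c and 7d fix which drugs qualify. The penicillins follow "Drugs included in the definition of penicillins are predefined as" and the cephalosporins follow "Drugs included in the definition of cephalosporins are predefined as". Neither list is offered as a set of examples, and neither ends with an entry for other members of the class.

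The same 13 penicillin names appear again in SAP section 10, Descriptive analysis, under "Proportion reporting allergy to any of the following indicated in Allergy field in eStar". SAP section 10, Main Analysis, also plans a same-admission penicillin-use proportion and a ratio of penicillin treatments to healthcare encounters, without saying which drugs count. Protocol section 8.0 names the outcome for penicillins in general and gives no list.

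**The concern.** A closed list makes every unlisted drug a non-qualifying drug. Oxacillin is a penicillin closely related to three that are listed (cloxacillin, dicloxacillin, nafcillin), and the SAP gives no reason for leaving it out. Cefotaxime and cefiderocol are likewise cephalosporins. These are facts of drug nomenclature, which the documents do not state.

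Under the stated rule, a patient whose only penicillin was oxacillin counts as not having received a penicillin. If de-labelling raises penicillin use, such losses would understate that effect. If the Main Analysis summaries use the same list, they would miss the same treatment. The ratio of treatments to encounters is the more exposed of the two, because it counts treatments: an unlisted course is lost there even when the patient also received a listed drug.

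**Working it through.** The plan states no figure for this endpoint, so there is none to reproduce. The stated 35 patients per group concerns label removal and does not use these lists.

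**Step 1. Check the names (SAP section 3, items 7c and 7d).**

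| List | Entries | Finding |
|---|---|---|
| Penicillins | 13 | No entry is oxacillin. The letters occur only inside cloxacillin and dicloxacillin, and an order for oxacillin matches neither name. |
| Cephalosporins | 19 | No cefotaxime, no cefiderocol, no entry containing ceftolozane. The nearest is "Ceftozolane-Tazobactam". |
| Penicillin allergy names (Descriptive analysis) | 13 | The same names as the penicillin list, again without oxacillin. |

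**Step 2. Who would be misclassified.** For the binary endpoint, only a patient who received an omitted drug and no listed drug in the same window. If penicillins and cephalosporins are scored together as one endpoint, the patient must have received none of 13 + 19 = 32 listed drugs, which makes the affected group smaller still.

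**Step 3. Size.** Let p0 and p1 be the true proportions of users in the control and intervention arms, and s the share of true users who received only omitted drugs, taken as equal in both arms. Observed use is p0(1 − s) and p1(1 − s). The difference becomes (p1 − p0)(1 − s). The odds ratio is recomputed from the reduced proportions, because SAP section 10 (Analysis of secondary endpoints) reports odds ratios. The documents give none of p0, p1 or s, so all values below are assumptions.

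| True use | s | Observed use | Difference (points) | Odds ratio |
|---|---|---|---|---|
| 10% vs 20% | 0 | 10.0% vs 20.0% | 10.0 | 2.25 |
| 10% vs 20% | 1% | 9.9% vs 19.8% | 9.9 | 2.247 |
| 10% vs 20% | 5% | 9.5% vs 19.0% | 9.5 | 2.235 |
| 10% vs 20% | 10% | 9.0% vs 18.0% | 9.0 | 2.22 |
| 30% vs 40% | 0 | 30.0% vs 40.0% | 10.0 | 1.556 |
| 30% vs 40% | 10% | 27.0% vs 36.0% | 9.0 | 1.521 |

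Worked example for the fourth row: (0.18/0.82) ÷ (0.09/0.91) = 0.2195 ÷ 0.0989 = 2.22.

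**Step 4. The misspelt entry.** The intended drug is on the list. Orders for it would be missed only if drugs were found by exact text string. The SAP does not state a matching method for this endpoint.

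**The case against.** The strongest reply is that nothing shows any patient is affected. The documents hold no formulary or usage data for oxacillin, cefotaxime, cefiderocol or ceftolozane-tazobactam at this centre, and zero misclassified patients fits everything in them. That stands. A reader might infer that some treatment is in fact scored as non-use; the documents support only that it would be, if it occurred.

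It can also be said that the misspelling is copy-editing. A drug code, a pharmacist or a chart reviewer would recognise the drug. That stands too, so no loss of data can be claimed from the spelling alone.

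A reader might further infer that allergy entries recorded simply as penicillin, or at class level, drop out of the baseline table because they match none of the 13 names. The text does not support this. The names sit beneath a parent item that counts any penicillin allergy in the allergy or problem list on the day of admission, and that item covers such entries. Nor does the primary endpoint refer to the drug list: it is defined by penicillin allergy labels in the chart.

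Finally, a fixed list is good pre-specification, and replacing it with an unnamed therapeutic-class code would be a preference and no clear gain. That also stands. The list can stay; its contents need correcting.

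What these replies leave untouched is the omission itself. The lists are closed, they leave out members of the two classes they define, and no reason is given.

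**Conclusion.** The point holds as a minor correction to one secondary endpoint. As written, a patient treated only with oxacillin would not count as a penicillin user, and one treated only with cefotaxime or cefiderocol would not count as a cephalosporin user. The Main Analysis penicillin-use summaries would share the penicillin omission if they use the same list.

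The effect is probably small. Even at an assumed 10% share the odds ratio moves by 0.03 to 0.04 (2.25 to 2.22, or 1.556 to 1.521), and the difference by one point in ten. This rests on an equal share in both arms, which is reasonable because one list serves both. Under that assumption the error is non-differential and pulls towards no effect. If the shares differed between arms, the direction would not be assured, but nothing in the documents suggests that they do. The primary endpoint, its test and the sample size are unaffected.

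**What to change.** Before the data are extracted:

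1. Add oxacillin to item 7c, and cefotaxime and cefiderocol to item 7d, or state that they are left out on purpose and why.
2. Correct "Ceftozolane-Tazobactam" to ceftolozane-tazobactam.
3. Make the penicillin names under Descriptive analysis agree with the corrected item 7c.
4. Say in one sentence that the Main Analysis penicillin-use summaries use the item 7c list.

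Timing matters more than effort. The trial is unblinded, so drugs added after use by arm has been seen would be a data-dependent choice. The cost is a few words in the SAP and the same change in the extraction query; no analysis, sample size or primary result changes.
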